Date: 10/06/2021

Official Title:

“Evaluation of a 4-month Online Lifestyle Intervention on the BMI Z-score of Mexican School Children During COVID-19 Pandemic: Randomized Controlled Pilot Trial”

NCT:

NCT04772859

Study Protocol Available¹: [name], [name], [name], [name], [name], [name], [name], [name]. Efecto de una intervención en línea de cambio en el estilo de vida sobre el puntaje zIMC de escolares mexicanos: protocolo de ensayo controlado aleatorizado piloto cegado a evaluadores durante la pandemia por COVID-19. Rev Esp Nutr Hum Diet. 2021; 25 (Supl. 2): e1320. doi: 10.14306/renhyd.25.S2.1320

ABSTRACT

Introduction: School closures due to the COVID-19 pandemic represent a risk factor for the development of childhood obesity, due to the increase in unhealthy behaviors. Online lifestyle interventions in schoolchildren could help to mitigate this problem. However, to our knowledge, no randomized controlled trials have been conducted to prevent obesity in schoolchildren during COVID-19. The aim of this study is to evaluate the effect of a 4-month online lifestyle intervention on the BMI Z-score of Mexican schoolchildren during the COVID-19 pandemic in an intervention group compared to a control group. **Material and Methods:** This is a protocol for an outcome assessor-blinded pilot randomized controlled trial. Schoolchildren from a public elementary school in Hermosillo, Sonora, Mexico will be invited to participate. Participants will be randomized to an intervention group (online lifestyle intervention) or a control group. The intervention will include online sessions of nutrition education and physical activity (60 minutes per session, 30 minutes for nutrition education and

30 minutes for physical activity) and nutrition information for parents. The control group will receive a digital brochure with nutrition recommendations at the beginning of the study and access to the program materials at the end of the study. The measurements will be performed at baseline and at 4 months. The primary outcome will be the BMI Z- score. Secondary outcomes: waist circumference, body fat percentage, nutrition knowledge, lifestyle parameters, participation, retention and acceptance of the intervention. The changes on the outcomes will be analyzed using an intention to treat analysis. The protocol was approved by the Research Ethics Committee of the University of Sonora Nursing Department and registered in Clinical Trials. **Conclusion:** To our knowledge, the study will provide the first evidence of the evaluation of online interventions for the prevention of obesity in schoolchildren derived from a randomized controlled trial, which could be crucial in the fight against childhood obesity.

INTRODUCTION

At the beginning of the year 2020, the World Health Organization declared the start of the COVID-19 pandemic. This is an infectious disease caused by the SARS-CoV-2 virus, which can cause mild symptoms to severe respiratory disease.² One of the strategies to mitigate infections has been social distancing and home confinement.³ This, among other consequences, has caused the closure of schools in different countries, affecting millions of students in the world.⁴ In Latin American and Caribbean countries, at the beginning of the pandemic it was reported that 95% of schools were closed due to COVID-19, affecting 156 million students of all levels.⁵

The schools closure can have consequences on the education and lifestyle of children and adolescents.⁶ It has been seen that when children are not in school (unstructured days), they gain more weight, compared to school days.^{7,8} This, due to an increase in the adoption of unhealthy behaviors, such as physical inactivity, more screen time, irregular sleep patterns and a high consumption of ultra-processed foods.⁹ Similarly, during the COVID-19 lockdown, unhealthy behaviors in

children have been reported. In a study with children and adolescents from Italy, it was found that during confinement they increased an average of 4.85 h/day in front of the screen and 0.65 h/day of sleep. On the other hand, the time of physical activity decreased by 2.35 h/week.¹⁰ In another study carried out in different countries in Europe and Latin America, it was found that children and adolescents increased their consumption of sweet beverages and fried and sweet foods, during confinement.¹¹

This is concerning, because about 340 million children and adolescents worldwide are overweight.¹² In Mexico, 35.5% of schoolchildren have overweight or obesity¹³, and this has both short- and long-term health consequences.^{14,15}

Different agencies have proposed lines of action to prevent child malnutrition during the pandemic. One of them is about the implementation of behavior change strategies to promote healthy eating and physical activity in children, using mass communication or technological resources.¹⁶

One option for providing health interventions is through the use of digital media. The "eHealth" consists of the use of Information and Communication Technologies (ICT) to promote health.¹⁷ The internet is one of the most used technologies by children and adolescents. It has been estimated that one in three children around the world uses the Internet for different entertainment and learning activities.^{18,19} This provides the opportunity to use interactive communication methods for the prevention of childhood obesity through the promotion of healthy behaviors.²⁰

Hamel & Robbins carried out a systematic review, of 15 studies of web based programs with children and adolescents with different change behavior theories frameworks. It was found that most of these programs were effective in modifying healthy eating behaviors such as: increased consumption of fruits, vegetables, and decreased calories and fat. Likewise, positive results in BMI and % body fat.²¹

These types of online interventions could represent a key strategy to prevent the development of childhood obesity during the current global health crisis. To our knowledge, to date there is no randomized clinical trial evaluating this type of program during the COVID-19 pandemic.

The present research group previously developed and evaluated a lifestyle change program focused on obesity prevention in Mexican schoolchildren in a face-to-face format, where positive results were obtained.²² Given the current situation due to COVID-19, this program was adapted to an online format to evaluate its effect through a pilot randomized controlled trial.

Explanation for the choice of comparators

The control group will be of children from the same public school as the children in the intervention group. The risk of contamination is reduced by not having face-to-face classes, but it is not completely eliminated, since there may be participants who take classes in the same group and interact online. Even so, the results will be valid if significant differences between groups are observed, as we observed in a previous study, because the previous situation would reduce the effect of the intervention.

OBJECTIVES

Primary objective

- To evaluate the effect of an online lifestyle intervention on the BMI Z-score of Mexican schoolchildren at 4 months during the COVID-19 pandemic in the intervention group compared to a control group.

Secondary objectives

- To evaluate the effect of an online lifestyle change intervention on waist circumference, body fat, physical activity and sedentary behaviors, food consumption, nutrition knowledge and quality of life of Mexican schoolchildren at 4 months during the COVID-19 pandemic in the intervention group compared to a control group.

- To evaluate the effect of an online lifestyle intervention on the retention, participation and acceptance of Mexican schoolchildren at 4 months during the COVID-19 pandemic in the intervention group.

MATERIAL AND METHODS

Study design

This is a pilot randomized controlled trial blinded to assessors, with 4-month follow-up. It is a pilot study, because we want to evaluate the effect and feasibility of the online intervention, to later carry out a definitive study considering an adequate sample size. The study will consist of two parallel arms, of superiority and with 1:1 allocation ratio.

To carry out this protocol, the SPIRIT 2013 guidewas followed.²³ The protocol was approved by the Research Ethics Committee of the Nursing Department of the University of Sonora (CEI-ENFERMERIA-EPM-003-2020) and registered on the Clinical.trials.gov platform (NCT04772859).

Participants

Children from a public elementary school in Hermosillo, Sonora will be invited to participate in the study. It is worth mentioning that this public school is not representative of all the schools in Hermosillo, Sonora. Hermosillo is a city of about 884,273 inhabitants and around of 392 public elementary schools. It is located in the state of Sonora, in northwestern Mexico. Because the program is entirely online, students who agree to participate will take the intervention from home.

Sample size

No studies of online lifestyle interventions to prevent obesity in schoolchildren during the pandemic were found to obtain the effect size and standard deviation needed to estimate the study sample size. So, we decided that it would be a pilot study of at least 50 participants and no more than 70. This was decided considering our logistical capacity, which implies measuring the response variables at home in a period of 2 weeks, in addition to being able to provide intervention, among other things. The invitation will be made to all students from fourth to sixth grade of a public school in Hermosillo Sonora.

Eligibility criteria

Sign the consent and informed assent and complete the anthropometric measurements and lifestyle questionnaires.

Inclusion criteria

- 4th, 5th and 6th grade students from the participating elementary school.
- Have access to the internet.
- Have an electronic device (eg computer, laptop, tablet or smartphone).
- Nutritional status: normal weight, overweight or obesity.

Exclusion criteria

- Have a medical condition that affects body weight.
- Taking medication that affects body weight.
- Take another intervention that affects body weight.
- Have a condition that prevents physical activity.
- Withdraw informed consent or assent.
- Have a sibling participating in the study.

Implementers

The lifestyle intervention will be implemented by a Nutritionist and two interns from the Bachelor's Degree in Physical Culture and Sports from the study team. In

addition, there will be the support of interns from the Nutritional Sciences Bachelor of the University of Sonora.

Interventions of the study

Online lifestyle intervention

The intervention will be based on the "Planet Nutrition" program. This program has a handbook that was previously developed by our study group and includes nutrition, physical activity, health, and behavior change strategies (Table.1). The program will last 4 months (March to July 2021). The components of the program will be: online nutrition education sessions, physical activity and family participation. It is worth mentioning that the nutrition education and physical activity sessions will be offered in the same 1-hour class. The first 30 minutes will be for nutrition education and the remaining 30 minutes for physical activity or games that involve movement.

Sessions	Topics
1	Creating healthy habits
2	What is excess weight?
3	Is it really bad to eat ultra-processed food?
4	The bitter truth of sweetened beverages
5	The importance of physical activity
6	Sedentary behaviors
7	Food Guidelines: My plate
8	Analyzing my healthy lunch
9	Jar for healthy drinking
10	Sweetened beverages vs healthy lunch
11	Reading food labels
12	Importance of healthy nutrition
13	Ultra-processed food

- 14 Sustainable lifestyle
- 15 Traditional Mexican diet
- 16 Healthy lunch
- 17 Identifying good and bad fats
- 18 What is important to know about sodium?
- 19 Smoking
- 20 Learning about Cancer
- 21 Importance of consuming fruits and vegetables
- 22 Vitamins and minerals
- 23 Why is fiber consumption important
- 24 Gut microbiota
- 25 Jeopardy: Let's put into practice the learning
- 26 How to prepare a salad
- 27 Learning to prepare healthy desserts
- 28 How to be active in summer holidays
- 29 Healthy nutrition in summer holidays
- 30 Balance christmas
- 31 Planet Nutrition challenge

Nutritional education sessions: Classes will be 3 days a week for 30 minutes each. Live sessions will be provided through the Zoom application, which is a platform for video conferencing. A code and password will be provided to access the private meeting. In addition, a web page of the study team (www.salud-nutricional.com) will be used to upload the topics that are seen in classes and activities for the participants. Presentations based on the “Planeta Nutrition” program handbook will be used. In addition, depending on the session, videos and

infographics will be made. In each class it is intended to take a little time to play a game, dynamic or workshop to reinforce learning.

The program will center on establishing health-related goals such as increasing consumption of fruits and vegetables, increasing physical activity time, decreasing hours spent in front of a screen, and reducing consumption of sweetened beverages. The program also will include the use of self-monitoring and positive reinforcement.

Physical activity sessions: Classes will be implemented 3 days a week for 30 minutes each. Children will work on developing different skills such as: flexibility, strength, elasticity and resistance. The Zoom digital platform will be used for the online (live) sessions. The classes will be recorded, in case the children want to do a class later.

Parent's participation: Parents who agree to participate in the program will be given a user to access a web page (www.salud-nutricional.com), where children's activities will be uploaded. This will be used to upload nutrition information, parenting activities, and study questionnaires. A private Facebook group will be created to upload teaching material (videos, infographics, messages and images) on a weekly basis. The difference between using the website and Facebook is that on the page the participants will be able to have the information ordered, upload their activities and study questionnaires. The topics addressed each week will be the same as those seen with the children in the nutrition sessions. On Facebook, they will have spaces for comments, questions, feedback and social support.

Control group: The control group will receive general nutrition recommendations at the beginning of the program, based on the Nutrition and Physical Activity Guidelines in the Context of Overweight and Obesity in Mexican Population.²⁴ A digital brochure will be sent in online format to the mail or through the WhatsApp application to parents. Upon completion of the study, they will be offered access to the materials from all the onlie lifestyle sessions, as well as physical activity videos for children recorded by the physical activity team.

Outcomes

The primary outcome is the change of the BMI Z-score from baseline to 4 months between the intervention group and the control group. The change in BMI Z-score for each individual will be obtained by subtracting the BMI Z-score value at 4 months minus the baseline value. The difference between groups will be obtained by subtracting the mean of the change in the intervention group minus that of the control.

Secondary outcomes will include the differences in waist circumference, body fat and relative fat mass, physical activity and sedentary lifestyle, quality of life, participation, attendance and nutrition knowledge. The categorical variables such as: food consumption and acceptance, will be evaluated with differences in proportions.

Recruitment

To invite the participants, school directors will first be contacted to invite them, inform them about the objectives and activities of the intervention. Fourth, fifth and sixth grade students from a public elementary school in Hermosillo, Sonora, Mexico will be invited to participate. It will seek to have a space in the students' online school classes, where parents will be invited to attend. A small presentation will be made with the invitation, objectives and activities of the intervention. During the same meeting, they will be sent via chat the link to a web page where they can find the the consent and informed assent and a personal data questionnaire to evaluate inclusion and exclusion criteria. They must be read and signed by parents and children online. Children may participate, even if the parents decide not to get involved in their part of the intervention.

Randomization

The measurements of the study will be carried out in a period of 2 weeks. Once the measurements are completed, the participants who meet the inclusion/exclusion criteria will be randomized to one of two groups: the “online lifestyle intervention” group or the control group. An independent person of the recruitment and

intervention of the study will receive a database, only with the codes and the basic variables of the study (BMI Z-score, sex and age) to perform the allocation of the participants. This will be based on a random block sequence, stratified by BMI Z-score and sex, with an allocation ratio of 1:1. The random number sequence will be generated using the randomization software available on the website: <https://randomizer.org/>. Since the assignment will be made in a single moment and without the knowledge of the participants, its concealment will be guaranteed. Participants will be explicitly informed to the assigned group.

Outcome measures

Study measurements will be performed at baseline and at 4 months. The primary outcome (BMI Z-score), waist circumference and triceps skinfold, will be measured by a person blinded to the allocation group and trained in the measurement of these variables. These anthropometric measurements will be carried out at the participants' homes in an outdoor area. Hygiene measures and recommendations will be followed to reduce the risks of contagion (use of NK95 face masks, plastic face shield, surgical suit, gloves, etc. short exposure time and disinfection of materials). Measurements will be made in less than 15 minutes. Before the home visit, a questionnaire will be sent to screen for possible symptoms related to COVID-19. Lifestyle questionnaires will be conducted online.

Primary outcome

- **BMI Z-score:** The measurement will be obtained using the sex, age, weight (kg) and height (m) of the participants. The height and weight will be combined (kg/m²) to obtain the BMI Z-score, expressed in units of standard deviation. Using The WHO Anthro Plus software.²⁵

Secondary outcomes

- **Weight:** To obtain the weight (kg), a TANITA SC-240 will be used. The measurement will be used to obtain the BMI Z-score.²⁶

- **Height:** The SECA 213 stadiometer will be used, following the Frankfurt plan. This measure will be used to obtain the BMI Z-score.²⁶
- **Waist circumference:** A Lufkin metallic anthropometric tape will be used. The umbilical scar will be taken as reference.²⁶
- **Body fat:** It will be estimated with the measurement of the tricipital skinfold, using a formula validated for Mexican children. To take the tricipital skinfold, the ISAK methodology will be followed.^{27,28}
- **Relative fat mass:** This is an estimator of total body fat. A formula carried out with children (8-14 years) will be used where the data of waist circumference (cm), height and sex (0 boys and 1 girls) will be needed.²⁹
- **Nutrition knowledge:** A questionnaire designed by the study team will be used to assess knowledge on nutrition. It consists of 32 questions on nutrition and health.
- **Food consumption:** Some questions from the semi-quantitative food frequency questionnaire from the National Health and Nutrition Survey were used.³⁰ We asked about the frequency of consumption of ultra-processed foods (sweet beverages, fried foods, cakes and cookies) and healthy foods (fruits, vegetables and water) in the previous 7 days. For each food, the size of the portion consumed was asked, considering an average portion established in the FFQ.
- **Physical activity and sedentary activities:** The physical activity and sedentary lifestyle part of the questionnaire “The Health Behavior in School-aged Children” (HBSC) was used, which is a validated lifestyle questionnaire for school-age children.³¹ It consists of 9 questions, 5 questions related to the time and frequency of physical activity and 4 to sedentary activities.
- **Nutrition knowledge:** a questionnaire designed by the research team (not validated) was used to assess the knowledge on nutrition and health. It consists of 32 questions with multiple choice answers. The results were evaluated on a scale from 0 to 10, the more correct answers, the greater score.

- **Quality of life:** The PedsQL™ (Pediatric Quality of Life Inventory) questionnaire was used, which was designed to assess quality of life aspects in both healthy pediatric patients (2 to 18 years old) and those with chronic diseases. The questionnaire consists of 23 questions about physical, emotional, social and school functioning. The responses are on a 5-point likert scale (never = 0 to always = 4). The score for each item is reversed and transformed to a linear scale of 0–100, with a higher score indicating a better quality of life.³²
- **Retention:** It will be evaluated with the percentage of participants (intervention and control group) who complete the intervention and the measurements at 4 months.
- **Participation or attendance of schoolchildren:** It will be evaluated with the percentage of attended intervention sessions and with the percentage of participants who attended all sessions.
- **Parent's participation:** At the end of the study, parents will be asked through an online questionnaire, the number of materials consulted from the program and will be reported as a percentage.
- **Acceptance.** Acceptability will be obtained with a questionnaire applied to children and parents to qualify the intervention, materials and benefits obtained with the intervention.
- **Personal information.** The first step for the screening of the participants consists of an online questionnaire of personal data. This will be sent at the time of the invitation to the program. Personal data of the child, internet access and electronic device, if they have a disease, if they take medications or perform extra interventions that may affect body weight will be asked. In addition, the email and education leve lof the parents will be asked.

Withdrawal of participants

Participants may withdraw from the study at any time they wish, being able to inform the reason or not.

Statistical Analysis

The normality of the data will be evaluated with the Shapiro Wilk test. Data will be presented as mean and standard deviation (mean \pm SD) or median and interquartile ranges according to their distribution. An independent samples t-test or Mann-Whitney U test will be used to analyze the difference in BMI Z-score and changes in secondary outcomes between groups. A chi-square test will be used to make comparisons on categorical variables. Two-tailed tests with $p \leq 0.05$ will be used as the criterion for statistical significance.

Data will be analyzed with an intention-to-treat analysis. If participants decide to withdraw from the intervention, they will be asked if the measurement at 4 months can be obtained to have at least the primary outcome for inclusion in the intention-to-treat analysis. If data is not obtained for any reason or subjects were excluded due to a protocol violation, they will be replaced by their baseline measurement.

Results will focus on change in the primary study variable (BMI Z-score), while changes in secondary variables and sub-analyses (sex and BMI: normal, overweight/obese) will be considered exploratory only. For data analysis, NCSS version 10 software (Number Cruncher Statistical System for Windows, Kaysville, UT, USA) will be used.

Confidentiality

Identifiable information and will be kept confidential. Each participant will be assigned a code, therefore, their identifiable information will appear with that code and not with names. Only the physical files will keep the names, which will be kept by the principal investigator of the study, in a safe place. Only the study team may have access to the database, for their purposes.

Declaration of interest

The authors did not report any potential conflicts of interest.

REFERENCES

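### Food consumption is to be compared as proportions; comparing intake adjusted for baseline would be more precise, and the plan should state how baseline answers are used for food (exploratory outcome, cheap improvement)

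*Combined protocol and SAP*

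**What the plan says.** - **Objective.** Secondary objectives lists the effect on "waist circumference, body fat, physical activity and sedentary behaviors, food consumption, nutrition knowledge and quality of life of Mexican schoolchildren at 4 months", against control. The programme sets "health-related goals such as increasing consumption of fruits and vegetables", and the same sentence names less consumption of sweetened beverages.
- **Data.** The Food consumption item under Outcome measures asks how often ultra-processed foods (sweet beverages, fried foods, cakes and cookies) were eaten, "and healthy foods (fruits, vegetables and water) in the previous 7 days". It adds: "For each food, the size of the portion consumed was asked, considering an average portion established in the FFQ". The response options are not shown.
- **Timing.** Outcome measures: "Study measurements will be performed at baseline and at 4 months". Eligibility criteria require the lifestyle questionnaires to be completed, so randomised children should have baseline answers.
- **Analysis.** Outcomes: "The categorical variables such as: food consumption and acceptance, will be evaluated with differences in proportions". Statistical Analysis: "A chi-square test will be used to make comparisons on categorical variables". The latter section also assigns a t-test or Mann-Whitney test to changes in secondary outcomes in general. It replaces 4-month data that were not obtained with the baseline measurement, and makes secondary variables exploratory.
- **Size.** Sample size: "it would be a pilot study of at least 50 participants and no more than 70", set by logistics.

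No section defines the food categories or cut-points, or says whether the proportions describe status at 4 months or change since baseline.

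**The concern.** Frequency and portion size can give an amount, or at least an ordered score, at two time points. Comparing proportions sets aside differences within a class, and the order of classes if there are three or more. As written for food, it also makes no stated use of each child's baseline answer. With 25 to 35 children per arm, that information is worth keeping.

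What is at stake is the precision of the dietary estimates. Diet is a direct target of the programme, and Study design says the pilot should lead to a definitive study, for which a difference in intake with its confidence interval would be useful. Undefined cut-points across six food groups also leave room for results to depend on cuts chosen after the data are seen.

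**Working it through.** **Inputs from the plan.** 50 to 70 children allocated 1:1, so 25 to 35 per arm (30 used as the central case); two-sided test at 0.05. The plan gives no power, effect size, SD or correlation for intake, so there is no stated figure to reproduce.

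**Assumed inputs.** True shift 0.5 SD at 4 months; correlation r between baseline and 4-month intake of 0.2, 0.4 or 0.6; normal intake, complete data; two classes cut at the control-arm median, fixed in advance.

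**Step 1: two-class chi-square.** The proportions above the cut are p0 = 0.500 and p1 = Φ(0.5) = 0.6915, a difference of 19.1 points. Exact binomial enumeration, without continuity correction, gives power of 31.2%, 32.6% and 36.5% at 25, 30 and 35 per arm.

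**Step 2: tests that keep the amount.** Approximate power is Φ(0.5 / (s × √(2/30)) − 1.96), with s = √(2(1−r)) for a test on change and s = √(1−r²) for 4-month intake adjusted for baseline (ANCOVA). For ANCOVA at r = 0.4, s = 0.917 and √(2/30) = 0.258, so 0.5/0.237 = 2.11 and power is Φ(0.15) = 56%. Simulation, which allows for the t distribution, gives slightly lower values:

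| 30 per arm, 0.5 SD | r = 0.2 | r = 0.4 | r = 0.6 |
|---|---|---|---|
| Two-class chi-square | 32.6% | 32.6% | 32.6% |
| t-test at 4 months | 47.6% | 47.9% | 48.0% |
| t-test on change | 32.4% | 41.5% | 56.8% |
| ANCOVA | 48.6% | 54.2% | 65.6% |

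ANCOVA minus chi-square: 16.0, 21.6 and 33.0 points. ANCOVA minus the test on change: 16.2, 12.7 and 8.8 points. At r = 0.2 nearly all of the gain over chi-square comes from not categorising (47.6 − 32.6 = 15.0 points). To match ANCOVA at 30 per arm, the chi-square test would need about 57 (r = 0.4) to 72 (r = 0.6) children per arm; the maximum here is 35.

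**Step 3: precision.** At 30 per arm the 95% CI for the 19.1-point difference is about ±23.9 points, so the half-width is 23.9/19.1 = 1.25 times the effect. For ANCOVA the half-width is 0.476 SD (r = 0.4) or 0.416 SD (r = 0.6), which is 0.95 or 0.83 times the 0.5 SD effect.

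**Step 4: coarse answers.** If the questionnaire yields four ordered classes, chi-square on the four classes has about 28% power. The baseline-adjusted score has 42.7%, 46.0% and 53.6% at r = 0.2, 0.4 and 0.6.

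**Step 5: baseline replacement.** Suppose the replacement rule applies to food answers and 15% of 4-month values are replaced (assumed). The expected difference falls to 0.85 × 0.5 = 0.425 SD. Power falls to about 25% for two-class chi-square and about 40%, 44% and 56% for ANCOVA at the three correlations.

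**Step 6: other settings (complete data, r = 0.4 to 0.6).**
- 25 to 35 per arm: chi-square 31% to 37%, ANCOVA 47% to 73%.
- Shift 0.3 SD: 15% against 24% to 30%. Shift 0.7 SD: 55% against 82% to 91%.
- Skewed intake analysed as log(1+intake): 34% against 52% to 64%. With 30% zeros: 34% against 46% to 53%.
- If the proportion means the proportion improved, chi-square has 28% to 39%.

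**The case against.** **A change test may already be planned.** Food consumption is a secondary outcome, and the general sentence in Statistical Analysis covers changes in secondary outcomes. A reader might infer from Outcomes that proportions are the only food analysis and that baseline is ignored; the documents do not support that as a certainty. Outcomes does place food apart from the outcomes compared as differences, so proportions remain the more natural reading. The objection stands in part: the sections need reconciling, and if a change test was meant, the gain is the smaller one in Step 2.

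**The team may have no continuous measure to lose.** The items come from a food frequency questionnaire whose response options are not shown. Calling food consumption categorical fits fixed response classes at least as well as it fits a cut continuous amount. This stands, and Step 4 is then the relevant comparison; the gain remains. Nor can a reader infer that portion size is dropped, because classes could be built from frequency and portion together.

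**The planned comparison is legitimate and exploratory.** Comparing proportions at 4 months is valid in a randomised trial and easy to read. Differences in proportions and a chi-square test do not conflict: one is the estimate, the other its test. Power is also a weak yardstick for a pilot sized by logistics. All of this stands, and it keeps the point to an improvement in precision.

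**Conclusion.** The point holds as a cheap, optional improvement. On the most natural reading, food consumption is compared in undefined classes with no stated use of baseline, although 7-day frequency and portion size are asked and measurement is scheduled at both time points. A baseline-adjusted comparison is more precise in every setting tried.

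The size rests wholly on assumed effects, correlations, cuts and distributions. In the central case with complete continuous data, the gain in power is about 16 to 33 points over chi-square, or about 9 to 16 if a test on change was intended. Against four coarse classes it is about 15 to 26 points (42.7 − 28 to 53.6 − 28). If 15% of values are replaced by baseline, all levels are lower and the estimated difference is diluted to about 0.43 SD.

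A reader might go further and conclude that the food analysis is invalid or that the trial's main result is weakened. The documents support neither: the planned comparison is valid, secondary outcomes are exploratory, and the primary BMI Z-score analysis is untouched.

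**What to change.** In Outcomes and Statistical Analysis, state one analysis for food consumption, so that the sentence on proportions and the general sentence on changes agree:

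- For each listed food (sweet beverages, fried foods, cakes and cookies, fruits, vegetables, water), compare arms on 4-month intake adjusted for baseline intake, with a 95% CI, labelled exploratory.
- Use weekly intake (frequency × portion) in a linear model on log(1+intake). If the questionnaire records only coarse classes, use the ordered score adjusted for its baseline score. Choose between the two from the questionnaire format, before results by arm are seen.
- Also show the result in children with observed 4-month answers, because replacement by baseline dilutes the difference.
- Keep chi-square for acceptance. If food proportions are also shown, fix their cut-points and time point in advance.

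**Cost.** Wording, one derived variable and one model per food; no new data. The log scale is harder to read than a proportion, skewed or coarse answers need handling, and frequency × portion may need conversion values because the response format is not shown.
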